### **I. Hypotheses and Specific Aims:**

Chronic irritability is a prominent dimension of pediatric psychopathology for which evidence-based treatments are scarce, have limited efficacy, or adverse side effects. There is a need to develop novel treatments, especially those that target the neurocognitive basis of irritability. One candidate is Interpretation Bias Training (IBT), a computer-based training designed to target rapid, automatic processing of social information. In a small open trial, IBT showed promise as an acceptable, feasible treatment for irritability. However, its underlying neurocognitive targets have not been established. In order to translate IBT for clinical use, we propose to examine two promising neurocognitive targets of IBT.

**Specific Aim 1:** Establish hostile interpretation bias as a treatment target for irritability and engage it through interpretation bias training. One hundred adolescents, drawn from an outpatient psychiatric clinic with varying degrees of clinically significant irritability, will be randomized to a session of active (n=50) or sham (n=50) IBT.

Hypothesis 1.1: The degree of hostile interpretation bias is positively associated with clinical irritability

Hypothesis 1.2: Active but not sham interpretation bias training will reduce hostile interpretation bias.

**Specific Aim 2:** Establish the ability to learn benign judgments of ambiguously hostile social information as a treatment target for irritability and engage it through interpretation bias training. A subsample of 50 participants (n=25 in each active and sham group) will train during fMRI.

Hypothesis 2.1: Learning rates during active IBT will be associated with baseline irritability.

Hypotheses 2.2, 2.3: In neural systems underlying threat learning, response while learning new associations during active IBT will be related to clinical irritability in terms of both neural activity (2.2) and functional connectivity (2.3).

[figure not shown]
**Exploratory Aim 3:** Provide preliminary evidence that changes in treatment targets are related to changes in irritability. To better establish the mechanism of target engagement and gather preliminary evidence for an efficacy trial, we will measure any changes in irritability after IBT. Therefore, we hypothesize that changes in irritability following active IBT will be associated with changes in hostile interpretation bias (hypothesis 3.1) and threat system response (hypothesis 3.2).

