The assessment uses “prototypical” male happy or angry expressions. These were created combining twenty males from the Karolinska Directed Emotional Faces set. Thirteen linear morphs between these expressions generated a set of 15 stimuli, or “morphs,” on a continuum from happy (morph 1) to angry (morph 15). All trials consist of a fixation cross (1000ms plus 500-6000ms jitter, mean 1500 ms), morph presentation (150 ms), visual noise mask (250 ms), and response screen with a question mark (until response). Participants respond via keypress with “angry” or “happy.” Each morph of the full set is presented three times in random order. Data from this assessment is used to estimate each participant’s balance point, or the point along the morph continuum where the participant’s judgments change from predominantly happy to angry.

The training is divided into six blocks. Timing and stimulus presentation are the same as in the assessment block except that feedback was provided after each response. Because some will train during fMRI, which does not allow indefinite timing, the response screen timing is 1500 ms plus 500-6000 ms jitter, mean 2000 ms. Feedback will be presented for 1500 ms. Active training is designed to shift the balance point (measured by a pretraining assessment) toward happy judgments of ambiguous faces. Participants receive positive feedback for rating as happy (and negative feedback for rating as angry) two ambiguous morphs nearest to the balance point and had been rated as angry by the participant during the assessment. Patients will receive encouragement to attend for nonresponses, which are anticipated to be rare. Similarly, sham training provided feedback based on the balance point measured at the beginning of each session during the pretraining assessment block. In the case of sham training, the feedback is designed to reinforce, rather than shift, the current balance point. Regardless of what the baseline balance point is, feedback never encourages incongruent judgments of the three extremes on each end of the morph continuum. Both conditions present each morph twice in random order during each training block. There are six training blocks, consisting of 30 trials each lasting 2.7 minutes. In the scanner, each block will begin with an additional 9.2s of fixation for pre-magnetization and end with an additional 12s of fixation to measure BOLD return to baseline.

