Hypothesis 1.2: Active but not sham, IBT will reduce hostile interpretation bias. Mixed-effects linear regression with balance point (interpretation bias) as a dependent variable and training condition (active vs. sham), and time of interpretation bias assessment (pre- or post-training) as independent variables of interest and person as a grouping variable and random effect. Similar models will test for group differences in active or sham IBT on other measures of hostile interpretation bias after training.

Hypothesis 2.1: The rate of learning new associations to ambiguous faces training will be associated with baseline irritability. For those in the active condition, linear regression will test the association between pre-training ARI (irritability) and learning rate to reversal feedback of baseline angry judgments to the two ambiguous morphs.

Hypotheses 2.2 and 2.3: Active, but not sham, IBT will evoke greater neural response in threat-learning systems. For each person, learning will be modeled with regressors coding the “value” or trialwise likelihood that a participant considers the morph to be angry. The amplitude of BOLD %signal change (activity) or amygdala covariance (generalized psychophysiological interaction; connectivity) related to these regressors represents neural response to value. Critically, these regressors represent learning itself where value is changing towards benign judgments in the active training condition to two ambiguous morphs. These will be carried forward to the second level mixed-effects linear models of the effects of morph by pre-training ARI by training condition. A voxel-wise threshold of  $p < .001$ , whole-brain, cluster corrected to  $p < .05$  via permutation testing or Monte Carlo simulation as appropriate, will be used to identify significant associations. A three-way interaction of change in value by morph by training condition will indicate neural areas where learning is influenced by irritability in active but not sham training of reversals of ambiguous morphs. In addition, our *a priori* identification of the likely role of the amygdala, OFC, and ACC justifies follow-up region-of-interest analyses of mean activity or connectivity extracted from these areas with the same omnibus mixed-effects model.

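### Aim 2 promises engagement but states only associations with irritability; the analysis plan rewords H2.2/2.3 as active versus sham and reads a term without ARI as an irritability effect

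*Combined protocol and SAP*

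**What the plan says.** Section I gives Aim 2 two tasks, to establish a target and to engage it: "Establish the ability to learn benign judgments of ambiguously hostile social information as a treatment target for irritability and engage it through interpretation bias training". The hypotheses listed beneath it are H2.1, "Learning rates during active IBT will be associated with baseline irritability", and H2.2/2.3, under which neural "response while learning new associations during active IBT will be related to clinical irritability", once for activity and once for connectivity.

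Section F gives the analyses. For H2.1: "For those in the active condition, linear regression will test the association between pre-training ARI (irritability) and learning rate to reversal feedback". For H2.2/2.3 the hypothesis becomes: "Active, but not sham, IBT will evoke greater neural response in threat-learning systems". Value-related BOLD amplitude or amygdala covariance is carried to "second level mixed-effects linear models of the effects of morph by pre-training ARI by training condition". The result is to be read as follows: "A three-way interaction of change in value by morph by training condition will indicate neural areas where learning is influenced by irritability". The rest of that sentence confines the influence to the active arm. The same omnibus model is then repeated in the amygdala, OFC and ACC.

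The description of the training session says of the comparator: "In the case of sham training, the feedback is designed to reinforce, rather than shift, the current balance point".

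**The concern.** Aim 1 makes the same two-part promise and has a hypothesis for each part: H1.1 is an association and H1.2 is active versus sham. Aim 2 in section I has only the first kind. Section F seems to supply the second kind for H2.2/2.3, but under the same hypothesis numbers, with a different null, and with a reading that returns to irritability.

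At stake is what Aim 2 may conclude. A positive result on the named term could be reported as an irritability finding, which it would not be. It could also be left out as evidence of engagement, which it would be. Section G says the study will provide the neurocognitive basis for a go/no-go efficacy trial, so the two conclusions should not be confused.

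**Working it through.** **1. The elements side by side (H2.2/2.3).**

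| Element | Contains ARI? | Contains active vs sham? |
|---|---|---|
| Hypothesis in section I | yes | no (active IBT only) |
| Hypothesis as restated in section F | no | yes |
| Second-level model | yes | yes |
| Named decisive term | no | yes |
| Reading given to that term | yes | yes |

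The restated hypothesis and the named term agree with each other. The section I hypothesis, the model and the reading all need ARI.

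**2. What the named term estimates.** The second-level outcome is already the response to value. A value by morph by condition interaction is therefore the morph by condition term at the second level: a difference between arms in how the value-related response varies over morphs. The term that carries irritability is morph by ARI by condition on the same outcome. The two can part company:
- If the arms differ by the same amount at every ARI, the named term is non-zero and irritability has no influence.
- If the ARI slopes run in opposite directions in the two arms and cross at the mean, irritability matters but the named term, evaluated at mean ARI, is zero.

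**3. What H2.1 can show.** It regresses a learning-rate parameter on baseline ARI within the active arm (planned n = 50). There is no comparator and no change score, so it can show association only. Comparing learning rates between arms is not a simple repair, because sham feedback reinforces the current balance point and gives no reversal of the ambiguous morphs to learn.

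**4. Size of the active-versus-sham contrast.** The only imaging figure in the Power analysis is 50 participants for 80% power at R² = .15, p = .05. It is not tied to a particular term.
- Reproduction, one term, noncentral F, f² = R²/(1 − R²) = .15/.85 = 0.176: 47 needed, and power 0.83 at N = 50. If .15 is taken as f² instead: 55 needed, and power 0.77 at N = 50. The stated 50 lies between the two.
- Active versus sham, 25 per arm, two-sided .05, 80% power: normal approximation d = (1.960 + 0.842) × √(2/25) = 2.802 × 0.283 = 0.79; by the t distribution, d = 0.81.
- For two equal groups d = 2√f², so R² = .15 corresponds to d = 2 × √0.176 = 0.84. The imaging power statement thus covers an arm contrast only if the difference is about that big. The Figure 3 caption calls d = 0.84 large.

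**The case against.** The strongest reply is that section F does contain an engagement analysis. Training condition is in the second-level model, both scanned arms enter it, and the named term, read literally, is an active-versus-sham contrast on the trained morphs, repeated in three prespecified regions. Background and section G name the second target as learning circuitry response, and the background speaks of engaging cortex during training. On that usage a neural condition contrast is relevant evidence, and no before/after change in learning rate is required. This stands. A reader might infer that no analysis in the plan bears on engagement; the documents do not support that. The contrast exists and is mislabelled.

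Two further inferences also go too far. One is that learning rate is estimated once and only in the active arm. The documents restrict only the H2.1 regression, and the computational-model paragraph sets no arm restriction; a single estimate per adolescent is a reasonable inference from one training session but is not stated. The other is that two nulls under one number inflate the false-positive rate. Nothing in the plan allows success to be claimed from either null, so no error rate can be attached.

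The named term may also be a drafting slip for morph by ARI by condition, since both can be called three-way. That is plausible, and section E describes the study as testing associations with irritability severity. But the text does not settle it, and the restated hypothesis, which also lacks ARI, points the other way.

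**Conclusion.** The point holds as a mismatch between hypothesis, model and interpreted term for H2.2/2.3, together with a limit on what H2.1 can support. As written, an irritability conclusion would be drawn from a term that does not contain irritability, and the contrast that does bear on engagement carries the wrong label. The finding rests on the wording and depends on no figure.

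The figure of about d = 0.81 assumes 25 analysable adolescents per arm, one contrast value per adolescent in a single region, and a two-sided .05 test without covariates. It does not describe the whole-brain analysis at the voxel-wise .001 threshold or the full mixed model. The matter should be settled before analysis, although the trial is small and not intended to assess clinical efficacy.

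**What to change.** In section F, under Hypotheses 2.2 and 2.3:

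- **Association.** Restore the section I wording (relation to irritability) and test it with the morph by ARI by condition term on the value-related response. Give the ARI slope within the active arm from the same fit, since that is what section I states.
- **Engagement.** Report the morph by condition term, with ARI mean-centred, as a separate, named neural engagement contrast. Without centring it refers to an ARI of zero, below the entry thresholds of 3 (parent) and 2 (self). State beside it that 25 per arm gives 80% power only at d of about 0.81 in a simple two-group comparison.

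In section I, state in Aim 2 that H2.1 supports association only.

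Optionally, describe acquisition in all 100 adolescents by a condition by block analysis of judgments of the two ambiguous faces (2 faces × 2 presentations × 6 blocks = 24 judgments each). This should be secondary. It overlaps H1.2, block 1 already contains feedback, and it measures shifted judgments rather than the ability to learn.

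The cost is wording in two sections and the reporting of terms from a model already planned. The downside is that the learning-rate part of Aim 2 is claimed more modestly.

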## II. Background and Significance:

**Significance.** Severe, chronic irritability currently affects approximately 3% of youth in the U.S. and is one of the most common presenting complaints to psychiatrists. Across 24 studies, chronic irritability in youth predicts later development of adult psychopathology, particularly depressive and anxiety disorders. It ranks among the strongest predictors of suicidality across the life span. The impairing nature and long-lasting adverse effects of chronic irritability underscore a critical need for effective treatments. Preliminary evidence suggests that interpretation bias training (IBT) may reduce irritability, yet this treatment remains undeveloped. To further develop this treatment, we propose to first establish its neurocognitive targets: hostile interpretation bias and learning circuitry response. The successful completion of this proposed research will establish the neurocognitive basis for a randomized controlled trial of the efficacy of IBT for clinical irritability. This contribution would be significant because it will further develop an evidence based, nonpharmacologic, and inexpensive treatment for irritability that targets specific neurocognitive mechanisms.

**Irritability and Hostile Interpretation Bias.** Prior work suggests, but has not established, that pathologic irritability is associated with hostile interpretation bias. Here, we use 'hostile interpretation bias' as an atheoretical, general term describing a tendency towards interpreting ambiguous social stimuli as threatening. It is also known as 'hostile attribution bias' and 'hostile attribution of intent.' Biased interpretations are automatic, that is occur rapidly and without awareness, and influence subsequent cognitive processes to promote a threat response. Hostile interpretation bias is a well-established cognitive correlate to two irritability-associated constructs: trait anger and a tendency towards aggression (association with aggression  $r=.17$  across 41 studies). In particular, the association between hostile interpretation bias and aggression increases with increasing severity of aggression. Hostile interpretation bias may be measured by a number of methods, often by biased judgments of complex social scenarios. However, to elucidate its neurocognitive underpinnings, recent work has measured hostile interpretation bias during judgments of ambiguous face-emotions. Using ambiguous face emotions, hostile interpretation bias was associated with a tendency towards expressing one's anger and low anger control in  $N=101$  undergraduates. I led a study reporting that, relative to youth without psychopathology, hostile interpretation bias was associated with disruptive mood dysregulation disorder (DMDD), a mental disorder characterized by severe, chronic irritability ( $N=89$ , Cohen's  $d=0.51$ , equivalent to  $r=.25$ ). Considering work in anger and aggression, this prior work converges to strongly suggest that irritability, across disorders, is positively associated with hostile interpretation bias (hypothesis 1.1).

**IBT to Treat Irritability.** Prior work suggests, but has not established, that irritability may be reduced by training against hostile interpretation bias. Interpretive biases are well-established targets of training programs to treat anxiety and depression, two phenomena with which irritability shares genetic, concurrent, and longitudinal associations. Indeed, irritability and anxiety share similar cognitive biases towards facial expressions signifying social threat. Following prior work in depression, an IBT program was developed to reduce anger and aggression with the presumptive target being hostile interpretation bias. IBT uses face emotions, mixtures of happy and angry expressions, as social stimuli (Figure 1). In two randomized controlled trials, two daily sessions of sham versus active computer-based training shifted participants' judgments of ambiguous facial expressions from "angry" to "happy." Active training was associated with decreased anger in healthy young adults and aggression in youth with conduct problems. In a small, open trial ( $N=14$ ), colleagues and I showed that four daily sessions of IBT was associated with reduced irritability in youths with DMDD. Both trials demonstrated a robust change in interpretation bias as measured by the same face-set stimuli used in training. However, there is no evidence that IBT results in generalized changes of hostile interpretation bias, i.e.

**Figure 1.** An interpretation bias training session. First the balance point is assessed. It is the point on a continuum of happy to angry faces where a person's judgments of them switch from predominantly happy to angry. Training sessions provide feedback on judgments that encourage happy judgments of two ambiguous faces previously judged as angry. Training effects are measured by another balance point assessment.

changes in interpretation bias to other face-set stimuli or other measures of hostile interpretation bias. Still, the effect of the training on symptoms related to hostile interpretation bias is compelling and supports further investigation to determine whether IBT reduces its intended target, hostile interpretation bias (hypothesis 1.2), under the NIMH plan for treatment development (Strategy #3.1).

**Learning and its Neural Correlates During IBT.** Impairments in learning during IBT may hinder an individual's ability to benefit from it. As part of our open trial of IBT on DMDD, we gathered preliminary evidence suggesting that the clinician-rated degree of improvement in irritability in youths with DMDD trended towards an association with the overall change towards more positive, i.e. "happy," judgments over the course of IBT ( $r=.49$ ,  $p=.08$ ). Thus, the effect of IBT on irritability may be moderated or mediated by a patient's ability to learn new valence associations to ambiguous facial expressions, i.e. capacity to train against their hostile interpretation bias. As described in the preliminary studies section below, we have evidence that youths with severe irritability are slower learners during IBT. As a first step towards investigating the role of the threat-learning system as a mediator of IBT treatment effect on irritability, we will test the hypothesis that pre-IBT irritability is associated with deficits in a person's ability to learn benign associations (hypothesis 2.1).

Learning during IBT should involve the neural threat-learning system, which includes the amygdala, anterior cingulate, and orbitofrontal cortex. Hostile interpretation bias is likely mediated by amygdala-enhanced detection of threat cues in ambiguous social information. To reverse these associations, IBT uses reinforcement learning against the biased judgments of social threat in ambiguous cues. Notably, we hypothesize that this would engage the orbitofrontal cortex to update the valence-associations of ambiguous information as well as the anterior cingulate cortex during unexpected feedback to perceived threat.

[figure not shown]
My colleagues and I recently published preliminary evidence suggesting that the lateral orbitofrontal cortex response to ambiguous expressions of happiness and anger changes after IBT in youths with DMDD (Figure 2). By combining computational modeling with functional magnetic resonance imaging (fMRI), we propose to directly test the involvement of the threat-learning circuit during training (hypotheses 2.2 and 2.3). If IBT's effect on irritability is mediated by learning, it follows that the degree of change in irritability is associated with the degree of change in hostile interpretation bias (exploratory hypothesis 3.1) and the threat-learning system response (exploratory hypothesis 3.2).

## Summary

Prior work strongly suggests an association between irritability and hostile interpretation bias (hypotheses 1.1). Earlier work also suggests IBT may reduce hostile interpretation bias, but only when hostile interpretation bias is measured by the same stimuli used in IBT. This study will assess whether a reduction in hostile interpretation bias generalizes (hypothesis 1.2). Prior work suggests, but has not proven that that irritable youth are slow to learn benign interpretations (hypothesis 2.1) and this is mediated by neural response (hypotheses 2.2 and 2.3).

